## 11.2 Reporting of adverse events

Adverse events must be reported by the physician on the NIS Safety Form in EDC.

The physician should record the diagnosis, if available. If no diagnosis is available, the physician should record each sign and symptom as individual adverse events. When a diagnosis becomes available, the diagnosis should be reported, and the signs and symptoms covered by the diagnosis should be described.

Several signs, symptoms or diagnoses can be reported on the same NIS Safety Form if they are part of the same clinical picture. This can be done by filling out one adverse event section per sign, symptom and diagnosis.

The physician must report adverse events (non-serious and serious) to Novo Nordisk within **3 calendar days** of the physician's knowledge of the event. Adverse events must be reported using the NIS Safety Form.

The physician must complete the NIS Safety Form in the EDC application within the above specified timelines of obtaining knowledge about the event(s). The physician must sign the form

Protocol  
 Study ID: NN8640-4515  
 UTN: U1111-1264-8642  
 EU PAS No: Pending

CONFIDENTIAL

Date:	15 February 2022	Novo Nordisk
Version:	3.0	
Status:	Final	
Page:	35 of 53	

within 7 days after completing the forms. If the EDC application is unavailable, paper forms must be filled out and forwarded electronically in an encrypted manner, or by fax or courier copies.

Contact details of Novo Nordisk affiliate safety responsible to which safety events should be reported if not reported through EDC will be supplied to the participating sites.

### 11.3 Adverse Events requiring additional data collection

The following AEs require additional data collection:

- Neoplasms (including all benign and malignant neoplasms)
- Medication Errors, misuse and abuse (misadministration) related to the study product treatment

For AEs requiring additional data collection, an event specific form should be completed in addition to NIS safety form regardless of seriousness of the event (note that full NIS safety form should be filled in for neoplasms within 3 calendar days regardless of seriousness of the event). Event specific forms should be filled and reported within **14 calendar days** of the physician's knowledge of the event.

### 11.4 Follow-up on safety information

All serious adverse events, serious adverse reactions and non-serious adverse reactions must be followed until the outcome of the event or reaction is "recovered", "recovered with sequelae" or "fatal" and until all queries have been resolved. Cases of chronic conditions, cancer, serious adverse reactions, serious adverse events or non-serious adverse reactions ongoing at the time of death (that is, the patient dies from another serious adverse event) can be closed with the outcome of "recovering" or "not recovered". Cases can be closed with an outcome of "recovering" when the patient has completed the study and is expected by the physician to recover.

All other non-serious adverse events must be followed until the outcome of the event is "recovering", "recovered" or "recovered with sequelae" or until the end of study, whichever comes first, and until all queries related to these adverse events have been resolved. Adverse events ongoing at time of death (that is, patient dies from another adverse event) can be closed with an outcome of "recovering" or "not recovered".

Follow-up information concerning previously reported adverse events must be reported by the physician on the NIS Safety Form **within 3 calendar days** of the physician's knowledge of the follow-up information.

All follow-up information requested by Novo Nordisk must be forwarded to Novo Nordisk within **14 calendar days** from the date specified on the request, unless otherwise specified in the follow-up information request.

The physician must ensure that the worst-case severity and seriousness is kept consistent through the series of forms used for safety reporting. The follow-up information should only include new (update and/or additional) information that reflects the situation at the time of the physician's signature.

Protocol  
 Study ID: NN8640-4515  
 UTN: U1111-1264-8642  
 EU PAS No: Pending

CONFIDENTIAL

Date:	15 February 2022	Novo Nordisk
Version:	3.0	
Status:	Final	
Page:	36 of 53	

## 11.5 Regulatory reporting requirements for adverse events

Sponsor's assessment of expectedness of adverse events is done according to the Company Core data sheet for Novo Nordisk product(s).

In addition, local expectedness assessment of adverse events is done according to local reference safety information document for reporting to national health authorities where required by local legislation.

## 11.6 Collection and reporting of technical complaints

Technical complaints on Sogroya® (somapacitan) which is considered related to an, according to study, collected adverse event/serious adverse event or adverse reaction/serious adverse reaction must be reported to Novo Nordisk along with safety information on the NIS Safety Form. Reporting timelines for technical complaints are the same as for reporting of adverse event/serious adverse event or adverse reaction/serious adverse reaction described in section [11.2](#).

Technical complaints NOT related to an adverse event/serious adverse event or adverse reaction/serious adverse reaction or technical complaints related to an adverse event not covered by the reporting requirements in section [11.1](#) may be reported to Novo Nordisk affiliate via the spontaneously reporting system.

## 11.7 Reporting of pregnancies in female patients and adverse events in pregnant patients, foetus or newborn infant

### Female patients:

Pregnancy must be reported on the paper pregnancy form **within 14 calendar days** of the physician's first knowledge of the pregnancy.

Elective termination of the pregnancy for medical reasons or any adverse events or pregnancy complications experienced by the pregnant female should be reported as AEs or SAEs on the NIS Safety Form within the timelines specified in section [11.2](#) for reporting of AEs/SAEs. Spontaneous abortion will always be considered a SAE and should be reported as such.

The outcome of the pregnancy and follow-up information on the newborn including medication during lactation should be reported on the designated pages of the paper pregnancy and pregnancy outcome form. Pregnancy outcome and follow-up information on the newborn should be reported **within 14 calendar days** of the physician's first knowledge of the pregnancy outcome and follow-up information. The physician must follow the newborn infant periodically until at least 12 months of age.

In case of abnormal pregnancy outcome, adverse events experienced by the foetus or newborn infant or adverse reactions in an infant exposed via breast milk then a paper NIS Safety Form should also be filled out using the patient identification of the Female patient (mother) followed by an "x" (e.g. 145060x) The timelines for reporting are the same as the ones specified in section [11.2](#) for reporting AEs/SAEs.

Paper forms should be sent by fax or encrypted email to: <Novo Nordisk Affiliate address >

Protocol  
 Study ID: NN8640-4515  
 UTN: U1111-1264-8642  
 EU PAS No: Pending

**CONFIDENTIAL**

Date:	15 February 2022	Novo Nordisk
Version:	3.0	
Status:	Final	
Page:	37 of 53	

## 11.8 Precautions/Over-dosage

For information concerning precautions and procedures to be observed in the event of overdose of Sogroya® (somapacitan) please see the latest edition of the SmPC or corresponding local product labelling text.

## 11.9 Novo Nordisk safety committee(s)

Novo Nordisk has an internal somapacitan safety committee that performs ongoing safety surveillance of Sogroya® (somapacitan).

The safety committee is a multi-disciplinary team with representatives from relevant functional areas that are necessary to provide integrated assessments of safety data from multiple sources for somapacitan. The members of the safety committee are highly qualified representatives of the respective departments and include e.g. medical specialists, non-clinical project manager, safety surveillance advisers and regulatory project manager/director. If relevant, internal and/or external ad-hoc members with specific area of expertise (e.g. neoplasms) may be invited to a safety committee meeting.

The somapacitan safety committee is responsible for reviewing the results of ongoing safety surveillance, for ensuring endorsements, and for validating signals and ensuring appropriate actions in case of new safety signals for somapacitan as well as for closing safety signals.

Signal management is an iterative process designed to detect, evaluate, manage, and communicate new risks associated with an active substance or whether known risks have changed.

## 12 Plans for disseminating and communicating study results

The information obtained during the conduct of this study is considered confidential and can be used by Novo Nordisk for regulatory purposes and for the safety surveillance of Sogroya® (somapacitan). All information supplied by Novo Nordisk in connection with this study must remain the sole property of Novo Nordisk and is to be considered confidential information. No confidential information must be disclosed to others without prior written consent from Novo Nordisk. Such information must not be used except in the performance of this study. The information obtained during this study may be made available to other physicians who are conducting other studies with the study product, if deemed necessary by Novo Nordisk.

### 12.1 Registration of study information

In accordance with Novo Nordisk's commitment to transparency in clinical activities, this study will be registered on 'ClinicalTrials.gov' and [www.novonordisk-trials.com](http://www.novonordisk-trials.com) no later than at enrolment of the first study participant. At least one study site per participating country will be included in the study registration.

For studies that include data collected also retrospectively, the study is to be registered prior to the first capture of data.

Protocol  
 Study ID: NN8640-4515  
 UTN: U1111-1264-8642  
 EU PAS No: Pending

**CONFIDENTIAL**

Date: 15 February 2022  
 Version: 3.0  
 Status: Final  
 Page: 38 of 53

**Novo Nordisk**

This non-interventional PASS must be registered in the EU Electronic Register of Post-Authorisation Studies (EU PAS Register) maintained by the European Medicines Agency and accessible through the European Medicines Agency's web portal.

If applicable the study will be registered at national study registries in addition to [www.clinicaltrials.gov](http://www.clinicaltrials.gov).

## 12.2 Communication and publication

Novo Nordisk commits to communicating or otherwise making available for public disclosure results of studies regardless of outcome. Public disclosure includes publication of a paper in a scientific journal, abstract submission with a poster or oral presentation at a scientific meeting, or by other means.

The final report will be published in the EU PAS registry and submitted to the respective regulatory authorities within 12 months after the end of data collection.

At the end of the study, one or more publication(s) may be prepared by physician(s) in collaboration with Novo Nordisk. Novo Nordisk reserves the right to postpone publication and/or communication for up to 60 days to protect intellectual property and reserves the right not to release interim results or data until a study report is available. The results of this study will be subject to public disclosure on external websites according to international regulations, as reflected in the Novo Nordisk Commitment to share information about clinical studies.

In a multi-centre study based on the collaboration of all study sites, any publication of results in a journal article must acknowledge all study sites. Where required by the journal, the physician from each site will be named in the acknowledgement.

The physician must ensure submission of the results of the study (either abstracts or full study report) to IEC/IRB (or other appropriate bodies as required locally) if the protocol or protocol abstract was submitted to any of these.

In all cases, the study results must be reported in an objective, accurate, balanced and complete manner, with a discussion of the strengths and limitations of the study. All authors will be given the relevant statistical tables, figures, and reports needed to support the planned publication. In the event of any disagreement about the content of any publication, both the physicians' and Novo Nordisk's opinions must be fairly and sufficiently represented in the publication.

Novo Nordisk maintains the right to be informed of any physician plans for publication and to review any scientific paper, presentation, communication or other information concerning the investigation described in this protocol. Any such communication must be submitted in writing to the Novo Nordisk study manager prior to submission for comments. Comments will be given within four weeks from receipt of the planned communication. For PASS studies in Europe, an advance agreement on publication policy between Novo Nordisk and physician allows the latter to independently prepare publications based on the study results. Also PASS studies in Europe require Novo Nordisk to communicate to the EMA and the competent authorities of the Member States in which the product is authorised the final manuscript of the article within two weeks after first

Protocol  
Study ID: NN8640-4515  
UTN: U1111-1264-8642  
EU PAS No: Pending

~~CONFIDENTIAL~~

Date: 15 February 2022  
Version: 3.0  
Status: Final  
Page: 39 of 53

**Novo Nordisk**

acceptance for publication. This is to allow national competent authorities to review in advance the results and interpretations to be published.

### **12.3 Physician access to data and review of results**

As owners of the study database, Novo Nordisk has discretion to determine who will have access to the database.

Provided that certain conditions are fulfilled, Novo Nordisk may grant access to information obtained during this study to researchers who require access for research projects studying the same disease and/or product studied in this study.

Protocol  
Study ID: NN8640-4515  
UTN: U1111-1264-8642  
EU PAS No: Pending

**CONFIDENTIAL**

Date: 15 February 2022  
Version: 3.0  
Status: Final  
Page: 40 of 53

## Appendix A

### Safety definition and evaluation of outcome, severity, and causality

#### Abuse

This corresponds to the persistent or sporadic, intentional excessive use of a medicinal product, which is accompanied by harmful physical or psychological effects

#### Adverse Event (AE)

Any untoward medical occurrence in a patient or clinical investigation subject administered/using a product and which does not necessarily have a causal relationship with this treatment. An AE can therefore be any unfavourable and unintended sign (including an abnormal laboratory finding), symptom or disease temporally associated with the use of a product, whether or not it is considered to be related to the product. An AE may be associated with the use of a drug, a medical device or both.

#### Adverse reaction (AR)

An Adverse reaction (AR) is a response to a medicinal product which is noxious and unintended. This includes AR which arises from:

- The use of a product within the terms of the marketing authorisation
- The use of a product outside the terms of the marketing authorisation, including overdose, off-label use, misuse, abuse and medication errors.
- Occupational exposure

An AR may be associated with the use of a drug, a medical device or both.

An AR is an AE for which the causal relationship between the product and the AE is suspected; that is judged to be possible or probable by either Novo Nordisk or the reporter.

#### Causality assessment

- Probable: good reason and sufficient documentation to assume a causal relationship
- Possible: a causal relationship is conceivable and cannot be dismissed
- Unlikely: the event is most likely related to an aetiology other than the Sogroya® (somapacitan)

#### Hospitalisation

When a patient stays at the hospital for treatment or observation for more than 24 hours. However, medical judgement must always be exercised, and when in doubt, the hospital contact should be regarded as a hospitalisation.

#### Medication error

A medication error is an unintended failure in the drug treatment process that leads to, or has the potential to lead to, harm to the patient. A failure in the drug treatment process does not refer to lack of efficacy of the drug, rather to human or process mediated failure.

Protocol  
 Study ID: NN8640-4515  
 UTN: U1111-1264-8642  
 EU PAS No: Pending

~~CONFIDENTIAL~~

Date:	15 February 2022	Novo Nordisk
Version:	3.0	
Status:	Final	
Page:	42 of 53	

Medication errors can therefore be:

- Associated with an AR
- Not associated with an AR
- An intercepted medication error ('near miss') is when an intervention caused a break in the chain of events in the treatment process before reaching the patient which would have resulted in a 'potential' adverse drug reaction. This intervention has prevented actual harm being caused to the patient; for example, a wrongly prepared medicine was actually not administered to the patient because the error was noticed by the nurse.
- A potential medication error which is recognition of circumstances that could lead to a medication error and may or may not involve a patient. The term potential medication error refers to all possible mistakes in the prescribing, storing, dispensing, preparation for administration or administration of a medicinal product by all persons who are involved in the medication process. An example is a pharmacist who noticed that the names of two medicines are similar and could clearly lead to product name confusion, but no patient was actually involved or has taken the medicine.

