Therefore, as part of the risk management plan for Sogroya® (somapacitan) as treatment of AGHD, the primary aim of this NIS is to characterise the long-term safety profile of Sogroya® (somapacitan) with special focus on the important potential risks (diabetes mellitus type 2, neoplasms and medication errors) and additional long-term safety information. Therefore, this PASS may allow a further evaluation of these potential risks in relation to treatment with Sogroya®. Medication errors are of specific interest since some patients will switch from daily GH injections to weekly injections with Sogroya®. Therefore, the PASS may provide information on whether this might lead to medication errors in clinical practice.

The secondary aim is to investigate the clinical parameters in patients treated with Sogroya® (somapacitan) on body composition, metabolic parameters, skeletal integrity, and quality of life. Clinical parameters will be analysed in specific sub-populations of AGHD patients, defined in protocol section [9.7.2.2](#) as these sub-populations have different starting doses of Sogroya® (somapacitan).

Protocol  
 Study ID: NN8640-4515  
 UTN: U1111-1264-8642  
 EU PAS No: Pending

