### 9.1.1.2 Secondary endpoints

#### 9.1.1.2.1 Safety

Endpoint title	Time frame	Unit
Number of Adverse Events (AEs)	From baseline (week 0) to end of study*	Count
Number of Serious Adverse Events (SAEs)	From baseline (week 0) to end of study*	Count
Number of Medication Errors (incorrect dose administration rate)	From baseline (week 0) to end of study*	Count

\*End of study will differ from patient to patient, but can be between 1 week and a maximum of 10 years

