**CONFIDENTIAL**

Date:	15 February 2022	Novo Nordisk
Version:	3.0	
Status:	Final	
Page:	26 of 53	

treatment when entering the study, details of titration regimen of Sogroya®(somapacitan) should be recorded in the eCRF when available. Patients' adherence will be recorded in the eCRF at each visit by an average missed dose per 2 months ( $\leq 1$  dose,  $1 <$  and  $< 3$  doses or  $3$  doses  $\leq$ ) based on physician asking the patient.

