### 9.7.2 Statistical methods

#### 9.7.2.1 Analysis of primary endpoints

The primary endpoints are the number of Adverse Drug Reactions (ADRs), incident neoplasms, and incident T2D from baseline (week 0) up to end of study (week 520).

Frequencies of ADRs during the study period will be summarised by MedDRA SOC and PT. This summary is displayed with number and proportion of patients with at least one event, number of event and event rate (events per 100 patient-years of exposure).

The primary objective of the study is to evaluate safety of once weekly dosing of Sogroya® (somapacitan) in AGHD patients over a study period up to 10 years, and analysis of ADRs will be one of the tools for achieving this. Adverse drug reactions will be analysed using descriptive statistics based on the ‘on treatment’ observation period (primary evaluation) and ‘in-study’ observation period (secondary evaluation) within the study period. The ADRs will be summarised by treatment, MedDRA (Medical Dictionary for Regulatory Activities) system organ class and MedDRA preferred term. The descriptive statistics will include the number and percentage of patients who experienced ADRs, the number of events and rate per 100 person years. ADRs will be listed by treatment and patient with information on severity, relationship to study product and demographics. ADRs with onset before first dosing will be reported in a separate listing.

In addition, incidence rates will be calculated for the endpoints Neoplasm and Diabetes Mellitus type 2.

Results will be reported separately for treatment-naïve and prevalent users of GH replacement therapy, and patients with a history of neoplasia and diabetes mellitus 2 will be addressed in stratified analyses.

For historical reference the primary evaluation, i.e. the on-treatment analysis, will be compared to the same results reported from the Nordinet® IOS database. It is not expected that there will be big differences in the baseline characteristics between the Nordinet® adult population and the population investigated in this study. If there are big differences between baseline characteristics, a matching procedure will be considered when making the comparison. In addition, a sensitivity analysis will be performed, restricting the primary evaluation to a European population only.

Protocol  
 Study ID: NN8640-4515  
 UTN: U1111-1264-8642  
 EU PAS No: Pending

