#### **Count-data secondary endpoints:**

The analyses of the following secondary endpoints will be performed both for the in-study and on-treatment observation period, in the same way as the analysis of the primary endpoint:

- Number of AEs
- Number of SAEs
- Number of medication errors (incorrect dose administration rate)

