# 11 Management and reporting of adverse events/adverse reactions

## 11.1 Collection of adverse events and other safety information

Safety definitions and a guideline for evaluation of outcome, severity and causality can be found in [Appendix A](#).

All adverse events including all fatal outcomes on Sogroya® (somapacitan) which occur after informed consent is obtained and until the end of study for each participating patient must be collected and reported to Novo Nordisk.

If the physician becomes aware of events of overdose, abuse, misuse, medication errors, lack of therapeutic effect or occupational exposure related to the study product treatment with or without an associated suspected adverse reaction, this should be reported to Novo Nordisk on the NIS Safety Form and on the medication error, misuse and abuse form (misadministration). These events will be summarised by Novo Nordisk in the interim and final study reports.

For female patients: Pregnancies and pregnancy outcome should be collected including **adverse events** in the pregnant patient, foetus or newborn infant from birth to 12 months of age.

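### The medication-error endpoint leaves open which errors count, and extra or mistimed injections after the daily-to-weekly switch are captured only by an open question or if the physician happens to learn of them

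*Protocol*

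**What the plan says.** Section 9.1.1.2.1 lists "Number of Medication Errors (incorrect dose administration rate") as a secondary safety endpoint, with unit count. Section 9.7.2.2 repeats the label and analyses the endpoint "in the same way as the analysis of the primary endpoint". Under section 9.7.2.1 that means patients with at least one event, plus "number of event and event rate (events per 100 patient-years of exposure"). Section 9.7.1 restricts the safety analysis set to patients exposed to Sogroya.

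Section 11.1 refers sites to Appendix A for safety definitions. Appendix A describes a medication error as an unintended failure in the treatment process that causes harm or could do so. Its list includes intercepted errors, where nothing was given to the patient, and "A potential medication error which is recognition of circumstances that could lead to a medication error and may or may not involve a patient".

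On why the endpoint matters, section 7 names medication errors as one of three important potential risks and says: "Medication errors are of specific interest since some patients will switch from daily GH injections to weekly injections".

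On capture:
- Section 11.1 makes reporting conditional: "If the physician becomes aware of events of overdose, abuse, misuse, medication errors, lack of therapeutic effect or occupational exposure".
- Section 9.2.6.2 has the patient asked about adverse events at each contact and offers one open question about problems as an example.
- Section 9.2.8.8 says adherence "will be recorded in the eCRF at each visit by an average missed dose per 2 months", in three bands, from the physician asking the patient.
- Section 11.3 requires an event-specific form once a medication error is reported.

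**The concern.** There are two gaps, of unequal weight.

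The first is in the definition. The label speaks of doses administered incorrectly, while the defined term reaches events in which nothing was administered or no patient took part. Sites will classify events over ten years in many countries using Appendix A. If the endpoint is tabulated from whatever they file, the rate will partly reflect local habit in reporting near misses and forgotten doses.

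The second is in ascertainment. Moving from a daily to a weekly injection could plausibly lead to injecting too often or at the wrong interval, as well as to omission. The protocol asks every patient, at every visit, about omission only. A patient who took an extra injection and felt well has no obvious reason to mention it. A low rate could then mean few errors or few reports, and the study could not tell which. Choosing categories at analysis can repair the first gap, but it cannot recover events that nobody elicited.

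**Working it through.** No stated figure is at issue, so the check compares the texts.

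**1. Do the categories in Appendix A fit the label and the analysis?**

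| Appendix A category | Incorrect dose administered? | Belongs to an exposed study patient? |
|---|---|---|
| Error that reached the patient, with or without a reaction | Possible | Yes |
| Intercepted error | No, it was stopped first | Usually identifiable, but nothing was given |
| Potential error | No | Not necessarily |

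An event with no patient cannot count towards patients with at least one event and has no exposure time. No sentence says which rows enter the endpoint. The title also combines a number and a rate, with unit count.

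**2. Where do missed doses belong?** Section 9.2.8.8 records them as adherence. Appendix A requires a failure that is unintended and at least potentially harmful, so deliberate omission falls outside. An unintentionally forgotten dose could meet the definition, and no text assigns it to one place.

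**3. How would each type of dosing error come to light?**

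| Type | Structured question at each visit | Other routes |
|---|---|---|
| Missed dose | Yes, section 9.2.8.8 | Open question; physician awareness |
| Extra injection or wrong interval | None written | Open question; physician awareness; overdose if the cumulative quantity exceeds the recommended maximum (Appendix A) |
| Wrong dose | None written | Open question; physician awareness; overdose if above the maximum |

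Section 9.2.8.8 also records the dose at entry and changes to dosing. It does not mention the interval at which the patient actually injected. The flow chart in section 9.2.6.1 has rows for dosing and titration and for adverse events, and none for medication errors. The form in section 11.3 is completed only after someone has recognised an error.

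**4. Is the period just after the switch visible?** Section 9.2.4 admits patients already on Sogroya. Section 9.7.2.2 plans an analysis of patients who switch after enrolment. For patients who switched earlier, any first errors may precede observation, because safety collection starts at consent. Pooled follow-up would therefore mix early and late time since switch.

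**5. Can the effect be sized?** The protocol gives no expected medication-error rate. The best adherence band is at most 1 missed dose per 2 months, which is 0 to 6 per patient-year (1 × 6), or 0 to 600 per 100 patient-years. That range starts at zero and comes from bands, not from counted events. Any ratio to true dosing errors would need an assumed denominator, so none is given.

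**The case against.** The strongest reply on definition is that the label is itself the restriction. Appendix A defines a reporting term for sites, and section 11.1 already has the broader reports summarised in the interim and final reports. A wide reporting term with a narrower endpoint is coherent, the analysis set tends to keep out events with no patient, and an analysis plan could settle the categories. Most of this stands. A reader might infer that near misses are certainly counted. The documents show only that the point is left open.

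A reader might also infer that every missed dose becomes a medication error and swamps the rate. That is not supported. Deliberate omissions are outside the definition, omissions have their own item, and a site would have to file a safety form and an event-specific form for each one. Only the unintentional omission is ambiguous.

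On capture, a reader might conclude that wrong-frequency errors are not collected at all. They are reportable, overdose includes cumulative excess, and a misadministration form exists. Its fields are not shown, so whether it records the type of error cannot be judged. Nor is it right that the study could say nothing about the switch: section 9.7.2.2 plans an analysis of patients switching after enrolment and separate results for treatment-naïve and prevalent users of growth hormone.

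Finally, the study is limited to routine-practice data, so prompting might be seen as a preference. However, the protocol already has the physician ask about missed doses at each visit. Asking about extra or mistimed ones in the same item is the same kind of activity.

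**Conclusion.** The point holds as a design weakness in a secondary endpoint. The mismatch of label and definition alone needs only a clarification. The firmer fault is ascertainment: the errors that motivate the endpoint have no structured prompt, while omissions do. Under-reporting of symptom-free extra or mistimed injections is likely, but this is a judgement. It assumes that patients seldom volunteer such events in answer to an open question and that the undisclosed form does not elicit them. Its size cannot be derived from the documents. Correction is worthwhile because medication errors are one of three named potential risks and the loss cannot be made good after data collection.

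**What to change.** 1. In sections 9.1.1.2.1 and 9.7.2.2, state that the rate counts errors that reached a study patient, with exposure time as denominator. List intercepted and potential errors separately, without a rate. State that missed doses are reported only under adherence.
2. In section 9.2.8.8, extend the per-visit adherence item to ask about extra, wrongly timed and wrong-dose injections since the last visit.
3. Tabulate the rate by time since switch to Sogroya, so that patients who switched before enrolment are not pooled with those observed from the start. This needs the date of first administration, which the observation periods in section 9.7.1 already presuppose.

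The cost is a few sentences, one eCRF item and one table. Active questioning will raise the reported count relative to spontaneous reporting, and the report should say so wherever the rate is set beside passively collected data.
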